Population characteristics: Participants who are 18 years or over, overweight, consume a poor quality diet and have one or more other risk factors for cardiovascular disease. Recruitment will take place over a 12-month period.

Participants will be considered eligible to enrol in the study if they are:

PAD-Q Study: Intervention Protocol

- **≥18 years AND**
- Overweight or obese (BMI >25 kg/m² and <45 kg/m²) **AND**
- have a low diet quality assessed using Prime Diet Quality Score (PDQS) (≤21) **AND**
one or more of the following risk factors for CVD:
 - current smoker
 - hypertension (whether pharmacologically managed or not)
 - hypercholesterolaemia (whether pharmacologically managed or not)

Exclusion criteria:

Participants will be ineligible to enrol in the study if they have:

- established CVD (i.e. MI, angina, heart failure, stroke, TIA, peripheral arterial disease or aortic disease)
- a medical condition which would substantially limit ability to complete study requirements (i.e. follow dietary advice and attend study site for data collection).
- following a medically prescribed diet or have a dietary restriction(s) that would substantially limit ability to complete study requirements (e.g. following a diet for management of Type 1 or Type 2 diabetes, weight loss, Coeliac Disease, Inflammatory Bowel Disease, food allergies or any other condition requiring significant dietary management).
- excessive alcohol consumption (>28 units/week for men or >21 units/week for women)
- currently pregnant
- no internet/email access (as this would impact on intervention delivery).
- unable to provide informed consent.

Recruitment

Participants will be recruited from the general population via established recruitment mechanisms. An electronic recruitment poster, email, and/or flyers will be circulated to workplaces and online notification systems e.g. church online bulletins, local online newspapers, online community notices (e.g. University of the Third Age) and social media outlets such as Twitter, Facebook and Instagram. A pop-up banner of the recruitment poster will also be produced and placed in entrance halls of public spaces/workplaces with appropriate permissions obtained. Contact details of the research team will be published on all study advertisements. Managerial permission will be obtained, where relevant, before any online advertisements are circulated or placed within workplace spaces. Recruitment will take place over a 12-month period.

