PAD-Q Study: Intervention Protocol

The Belfast site will recruit n=85 participants according to the inclusion and exclusion criteria. The UCD site will recruit 49 participants.

Those who are interested in taking part in the study after reading the study advertisement will be directed to make contact with the research team. The initial screening process will involve asking participants to complete a screening questionnaire (incorporating all aspects of inclusion/exclusion criteria and collection of contact details) via telephone with the researcher. The screening process will rely on self-reported information obtained from the participant and should take approximately 20-30 minutes to complete. After the telephone call, researchers will review responses within the screening questionnaire and email a link to the Participant Information Sheet to those identified as potentially eligible to take part.

After being given at least 48 hours to read the Participant Information Sheet, the researcher will telephone the participant to discuss the research in further detail and ensure the participant fully understands the study information, implications of involvement and answer any questions they might have. If the participant agrees to participate, they will be invited to complete their consent online and attend the Centre for Public Health for baseline data collection.

Study design and assessments

This is a single-blind randomised controlled parallel group dietary intervention, conducted over 6 months in participants at high risk of cardiovascular disease living on the island of Ireland, to evaluate the efficacy of personalised dietary advice, based on both food biomarkers and a diet quality assessment, in improving diet quality and cardiometabolic outcomes.

Study randomisation will be conducted centrally for both sites (Northern Ireland and Republic of Ireland). Once participants have completed their baseline visit, they will be randomized (randomization scheme generated using www.randomization.com with random block sizes) to either control or intervention group. Participants will be stratified by gender and diet quality. Participants will be unaware of which group they have been randomised to. Control participants will be offered personalised dietary advice at the end of the intervention:

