1) ***Control*** – participants will be given conventional dietary advice based on current regional population dietary recommendations via email to encourage dietary change towards a better quality diet. Participants will be given the dietary advice at baseline (4 messages) and month 3 (4 messages) of the intervention. Control participants will be offered personalised dietary advice at the end of the intervention.

2) ***Personalized dietary advice*** – participants will be encouraged to make dietary change using individualized recommendations incorporating both food biomarkers and diet quality assessment

PAD-Q Study: Intervention Protocol (assessed using PDQS questionnaire). Based on these biomarker data and the diet quality assessment, a system of categorization will be developed and decision trees created to ensure standardized delivery of advice within this intervention arm. In this way, the intervention will be standardised across sites. Relevant behaviour change techniques (BCT), i.e. the BCT framework and the CALOR-E diet and physical activity-specific taxonomy^{11,12} have been integrated into the intervention development. Dietary advice will be delivered via email in both groups.

Participants will commence on the intervention within one month of their baseline visit. This will enable researchers to collect, process and analyse urine samples to help inform the dietary advice given as part of the intervention.

Dietary advice will be delivered via email. Both groups will receive dietary advice at baseline and month 3. Both groups will receive contact from the research team at months 0, 1, 3 and 6 months via email. The control group will be offered personalised dietary advice at the end of the intervention. As such, the frequency and duration of contact will be similar in both groups.

Outcome measures:

Outcomes will be assessed during a study visit at 0, 3, and 6 months and maintenance data will be collected online at 12 months for the primary outcome.

Primary outcome:

- Change in dietary quality assessed by Prime Diet Quality Score (PDQS). This will also be assessed six months after the intervention completes, to determine whether the intervention influences longer term adherence to a better quality diet. (assessed at 0, 3, 6 and 12 months). The 12 month PDQS (6 months post intervention) will be collected online).

Secondary Outcomes:

1. Change in markers of cardiometabolic risk including:

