Based on published US data, with a standard deviation (SD) of PDQS of 2.3, as previously seen¹³, and an assumption of a difference in increase in PDQS of 5 between the personalized dietary advice and control groups, then, if we have 60 participants in each group, the study would have over 90% power to detect this difference in mean PDQS as statistically significant, at the $\alpha=0.05$ level. We will recruit 134 participants in total to allow for approximately 10% drop-out. For the health outcomes, and, based on what was observed in a dietary intervention study on improving diet quality in similar, high CVD risk participants¹⁴, if we have 60 participants in each group, and we assume that (i) the SD of the change in diastolic blood pressure (DBP) is 9 mmHg at the end of the study; (ii) a difference in DBP of 4.5 mmHg between the personalized dietary advice and control groups; then the study would have 80% power to detect, as statistically significant at the 5% level, these differences in mean change between the two groups. We will have similar levels of power (~80%) to detect effect sizes of similar magnitude in total cholesterol, HbA1c, and body weight. The analysis of gut microbiota composition and functionality will be exploratory in nature.

Statistical analysis

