The repeated end-point measures generated by the study design will be analyzed with techniques appropriate for longitudinal data using the xt panel study procedures available in Stata release 11 (College Station, TX). Initial examination of the correlation structure of the repeated measures will help guide model fitting. The influence of the dietary intervention under study will be assessed by comparing the means of changes in measurements from baseline to 6 months between the personalised dietary advice and control groups. This difference in means will provide an estimate of the effect of intervention and 95% confidence limits will be calculated to indicate its precision. If appropriate, measurements will be logarithmically transformed prior to analysis and interpretation will be made in ratio terms on the original scale. Compositional analysis of whole metagenome and metatranscriptome datasets will be performed using the read-based bioinformatics analysis suite, including the HUMAnN2158 analysis network¹⁵, MetaPhiAn2 profiler¹⁶ and KneadDATA pipeline, developed in the Huttenhower laboratory at Harvard T.H. Chan School of Public Health. Testing for differences in microbial features between intervention and control groups will be performed with the MaAsLin sparse regression method¹⁷. It is unknown whether men and women respond differently to the same diet, in terms of food biomarker profiles and CHD risk. In previous cohort studies conducted by the research teams, similar associations of various diet quality indices were observed with risk of chronic diseases between men and women¹⁸⁻²¹. In the current study, we consider both men and women, and whenever appropriate, we will perform gender-specific analyses to assess gender difference. We will combine the data of men and women when the test for interactions by gender is not significant, and gender will be adjusted as a covariate.

Process Evaluation

A process evaluation will be conducted at the end of the 6-month study to help elucidate if, how and why the intervention worked. A process evaluation framework for the PAD-Q trial has been developed based on both the Medical Research Council guidance²² and RE-AIM framework²³.

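### The 6-month effect is a difference in mean change with no adjustment named for the outcome's baseline value, the diet-quality stratum or site; a baseline-adjusted model would be more precise using data already collected

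*Combined protocol and SAP*

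**What the plan says.** The Statistical analysis section of the combined protocol and SAP says that repeated measures will be "analyzed with techniques appropriate for longitudinal data using the xt panel study procedures available in Stata release 11", with the observed correlation structure helping to guide model fitting. It lists no model terms. It then gives one definition of the effect: "comparing the means of changes in measurements from baseline to 6 months between the personalised dietary advice and control groups", reported with 95% confidence limits.

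One covariate is named. Men and women are combined when the gender interaction is not significant, "and gender will be adjusted as a covariate"; otherwise gender-specific analyses are planned.

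Under Study design and assessments: "Participants will be stratified by gender and diet quality". The same section says "Study randomisation will be conducted centrally for both sites"; the targets are 85 participants in Belfast and 49 in Dublin. Under Outcome measures: "Outcomes will be assessed during a study visit at 0, 3, and 6 months". The baseline value of each outcome will therefore exist.

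**The concern.** A change score fixes the coefficient on the baseline value at 1. A baseline-adjusted model estimates that coefficient from the data. Unless the true slope is 1, the change score carries avoidable noise. In addition, one of the two randomisation strata (gender) is carried into the analysis and the other (diet quality) is not. Leaving out a prognostic stratifier tends to make intervals too wide, which is conservative but wasteful.

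Bias is not at stake. What could be lost is precision on the cardiometabolic outcomes. The Power section works at 80% for DBP and at about 80% for total cholesterol, HbA1c and body weight, so there is little margin to give away.

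**Working it through.** **Inputs from the Power section.** 60 analysed per arm; DBP difference 4.5 mmHg; for its spread, "the SD of the change in diastolic blood pressure (DBP) is 9 mmHg at the end of the study"; significance level 5%; PDQS difference 5 and SD 2.3. The plan does not say whether 2.3 is an SD of change; it is read that way here. Tests are taken as two-sided.

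**Assumed, because the documents do not give it.** The correlation rho between the baseline and 6-month values: 0.3, 0.5, 0.7 and 0.9.

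**Step 1: the plan's own figure.** Standardised difference for DBP = 4.5/9 = 0.5. With 60 per arm, power is 78.2% by the normal approximation and 77.5% by the noncentral t. Both are close to the stated 80%; 64 per arm would be needed to reach 80% by the t calculation. PDQS power at a difference of 5 and SD 2.3 is about 100%, consistent with the stated figure of over 90%.

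**Step 2: variances.** Let s0 and s1 be the SDs at baseline and at 6 months.

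- Change score: s0² + s1² − 2·rho·s0·s1
- Baseline-adjusted: s1²(1 − rho²)
- Change score minus adjusted: (s0 − rho·s1)², which is never negative

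With s0 = s1 = s these become 2s²(1 − rho) and s²(1 − rho²), so the ratio of adjusted to change-score variance is (1 + rho)/2.

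**Step 3: DBP.** Change-score half-width = t(118) × 9 × √(2/60) = 1.980 × 1.643 = 3.25 mmHg. For the adjusted analysis, the SD of 9 is multiplied by √((1 + rho)/2).

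| Analysis | Variance ratio | Power | 95% CI half-width (mmHg) | n per arm for 80% power |
|---|---|---|---|---|
| Change score | 1 | 77.5% | 3.25 | 64 |
| Adjusted, rho 0.3 | 0.65 | 92.1% | 2.62 | 42 |
| Adjusted, rho 0.5 | 0.75 | 88.0% | 2.82 | 49 |
| Adjusted, rho 0.7 | 0.85 | 83.8% | 3.00 | 55 |
| Adjusted, rho 0.9 | 0.95 | 79.6% | 3.17 | 61 |

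**Step 4: the price of adjustment.** Using 114 instead of 118 degrees of freedom changes power by no more than 0.001. Chance imbalance in k covariates inflates the variance by about 1 + k/(N − k − 3). For k = 4 and N = 120 that is 1 + 4/113 = 1.035. Taking both together, and supposing that the three covariates other than baseline explain nothing, the powers become 91.2%, 86.9%, 82.5% and 78.2%. All remain above 77.5%. Measured by interval width, the break-even rho is about 0.98 with one covariate and 0.93 with four.

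**Step 5: PDQS.** Change-score half-width = 1.980 × 2.3 × √(2/60) = 0.83 points. Entry requires a PDQS of 21 or less, which narrows the baseline spread. With slope b, residual variance 1 − b² and baseline variance k (relative to an unrestricted value of 1), the variance ratio is (1 − b²)/[(1 − b²) + k(1 − b)²]. At an assumed b = 0.5:

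- k = 1: 0.75/(0.75 + 0.25) = 0.75, half-width 0.72
- k = 0.5: 0.75/(0.75 + 0.125) = 0.857, half-width 0.77
- k = 0.25: 0.75/(0.75 + 0.0625) = 0.923, half-width 0.80

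The gains from adjusting for the diet-quality stratum and for site cannot be quantified from the documents.

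**The case against.** The strongest reply is that the plan is under-specified and not wrong. It commits to longitudinal methods, and a difference in mean change can itself be estimated with baseline in the model; the treatment effect is then the same as when the 6-month value is modelled. That is correct, and the wording on Stata procedures does leave the option open. But it names no terms and defers the choice until data are seen, while the one estimator written down is the difference in mean changes. Naming the model settles the matter.

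Four further points stand in part.

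- **Cost.** Adjustment is free in participants and data but not in statistical terms. Step 4 shows that chance imbalance removes up to about 1.5 power points, and a very highly correlated outcome would gain nothing.
- **Site.** It is not a stratification factor. Adjusting for it is good practice in a two-centre trial; the case for the diet-quality stratum is stronger because the design uses it.
- **Redundancy.** If the stratum is a grouping of baseline PDQS (no cut-off is given), it will add little to the PDQS model beyond the baseline value. It may still matter for the other outcomes.
- **Model form.** The figures above are for an analysis of the 6-month visit alone. A mixed model with a single baseline slope for both visits loses a little. With equal variances scaled to 1, a common slope 0.1 away from the best 6-month slope adds 0.1² = 0.01 to a residual variance of 0.75 at rho 0.5.

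Finally, the primary conclusion is not at risk at the assumed 5-point difference. That limits how serious the point is; it is not a reason to keep the less precise estimator.

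**Conclusion.** The concern holds, as a recommended improvement in efficiency and pre-specification. The stated estimator is unbiased but generally less precise than one adjusted for data the trial already collects. For DBP the gain runs from about 14.6 power points at rho 0.3 (92.1 − 77.5) to about 2 at rho 0.9 (79.6 − 77.5). If four covariates are charged in full, the gain at rho 0.9 shrinks to under 1 point (78.2 − 77.5). For PDQS the benefit is a half-width of 0.72 to 0.80 instead of 0.83, with no material change in power.

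These sizes rest on assumed correlations, equal variances at the two times for DBP, two-sided tests and 60 analysed per arm. The direction does not depend on the chosen correlation, except at values so high that the small cost of estimating the covariate effects outweighs the gain.

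**What to change.** Replace the effect definition in the Statistical analysis section with wording such as:

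> The 6-month effect will be estimated from a linear mixed model of the 3- and 6-month outcomes with treatment, visit and treatment-by-visit terms, adjusted for the baseline value of that outcome, gender, diet-quality stratum and site.

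Report the adjusted 6-month difference with its 95% confidence interval as the effect estimate, and keep the raw comparison of mean changes as descriptive. A baseline-by-visit term may be added so that the baseline slope can differ between visits.

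The cost is a change of analysis wording and a few degrees of freedom. Baseline values, gender, stratum and site are already recorded, and randomisation, visits and sample size are unchanged.

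### The plan does not say that the pooled intervention effect stays primary when the gender-interaction test is significant, so that test could choose the reported effect

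*Combined protocol and SAP*

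**What the plan says.** The Statistical analysis section of the combined protocol and SAP compares mean changes from baseline to 6 months between the two arms and states: "This difference in means will provide an estimate of the effect of intervention". No gender condition is attached at that point.

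Later, after the microbiome methods, the section turns to gender. It opens with "It is unknown whether men and women respond differently to the same diet, in terms of food biomarker profiles and CHD risk", continues that "whenever appropriate, we will perform gender-specific analyses to assess gender difference", and ends with the operative rule: "We will combine the data of men and women when the test for interactions by gender is not significant". In the combined analysis, gender is a covariate.

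Three things are not stated:
- what the main result is when the interaction is significant;
- the level at which the interaction is tested;
- what would count as success on gender-specific results.

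The lead-in mentions biomarkers and CHD risk rather than PDQS, but the rule excludes no outcome.

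The Power section uses a 5% level, but only for the comparison between arms: "as statistically significant at the 5% level, these differences in mean change between the two groups". Under Study design and assessments, "Participants will be stratified by gender and diet quality".

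**The concern.** Looking at an intervention-by-gender interaction is reasonable. The difficulty is that combining men and women is made conditional on the result. If the condition fails, the plan leaves open whether the whole-sample effect is still the result, still shown, or replaced by two gender-specific effects.

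If it is replaced, a preliminary test on the same data has chosen the reported effect. The error rate of the whole procedure then depends on a success rule that the plan does not contain. A pooled estimate that is unbiased and adequately powered could also drop out of the conclusion because of a chance interaction.

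**Working it through.** **Inputs from the Power section.** 60 per arm. PDQS: difference 5, SD 2.3, level 0.05. Diastolic blood pressure (DBP): difference 4.5 mmHg, SD of change 9 mmHg, 5% level.

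**Assumptions, because the plan is silent.** Two-sided tests; interaction tested at 5%; larger gender 50% to 80% of the sample; 1:1 allocation and equal SD within each gender. Two success rules after a split are tried: either gender significant, or both significant in the same direction.

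**Step 1: reproduce the plan's power.**
- DBP: SE = 9 × √(2/60) = 1.643; 4.5/1.643 = 2.739; power = Φ(2.739 − 1.960) = 0.782 (0.775 by the t-test), against 80% stated. Close.
- PDQS: SE = 2.3 × √(2/60) = 0.420; 5/0.420 = 11.9; power above 0.999, consistent with the stated figure of over 90%.

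**Step 2: write down the rule.** Let z_P be the pooled, gender-adjusted statistic and z_I the interaction statistic. Under the assumptions these are independent. With gender shares f and 1−f, the gender-specific statistics are

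z_1 = √f · z_P + √(1−f) · z_I and z_2 = √(1−f) · z_P − √f · z_I.

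If |z_I| ≤ 1.96, z_P is tested; otherwise z_1 and z_2 are tested, all at two-sided 5%. With no true interaction, 5% of trials split by chance, so

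overall rate = 0.95 × (pooled rate) + 0.05 × (rate among split trials).

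The rates among split trials come from simulation (normal model, 4 million draws per setting).

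**Step 3: false-positive rate with no effect in either gender.** Unsplit trials contribute 0.95 × 0.05 = 0.0475.

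| Success rule | Rate among split trials | Overall |
|---|---|---|
| Either gender, 50:50 | 0.650 | 0.0475 + 0.05 × 0.650 = 0.080 |
| Either gender, 80:20 | 0.714 | 0.0475 + 0.05 × 0.714 = 0.083 |
| Both, same direction | 0.0000 to 0.0004 | 0.0475 (about 4.7%) |
| Pooled effect always stands | not applicable | 0.050 |

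**Step 4: DBP power with a true 4.5 mmHg in both genders.** Unsplit trials contribute 0.95 × 0.782 = 0.743. Split trials can add at most 0.05, so overall power lies between 0.743 and 0.793 whatever the success rule. Simulated: 0.792 (either), 0.744 to 0.750 (both), against 0.782 pooled.

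**Step 5: PDQS power.** In the smaller gender at 80:20 there are 12 per arm: SE = 2.3 × √(2/12) = 0.939; 5/0.939 = 5.32; power = Φ(5.32 − 1.96), above 0.999. Even the stricter rule costs essentially nothing at the plan's inputs.

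**Step 6: what is lost in a chance split.** Because z_P is independent of z_I, the pooled DBP estimate still averages 4.5 mmHg in split trials. The gender estimates do not. At 50:50 the interaction SE is 9 × √(2/30 + 2/30) = 3.286. The mean of |z_I| given a split is 2φ(1.96)/0.05 = 2.338, so the mean gap is 2.338 × 3.286 = 7.68 mmHg. The two estimates therefore average 4.5 ± 3.84, about 8.3 and 0.7 mmHg.

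**Finite-sample check** (t-tests with estimated SD, 1 million trials per setting). Null: 0.080-0.081 either, 0.047 both, 0.049-0.050 pooled. DBP power: 0.785 either, 0.737-0.743 both, 0.775 pooled. The conclusions do not change.

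**The case against.** The best reply is that the plan already defines the effect without any gender condition, powers only that whole-sample comparison, and brings in gender later as a subgroup question. Nothing says the first estimate is withdrawn. This reading is tenable, and it is why the adverse reading is called plausible rather than certain. It does not settle the matter, because the closing sentence makes combining conditional and no other section says that the pooled effect survives a significant interaction.

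Three further objections stand and limit the point:
- **The false contrast between genders is not caused by the rule.** Any interaction test at 5% fires by chance in 5% of trials. The 8.3 versus 0.7 mmHg pattern would still appear if gender-specific results were only supportive. What changes is whether the pooled estimate is kept and governs the conclusion.
- **The success rules are assumptions.** They disagree even on direction: one raises the error rate, the other lowers it slightly.
- **The effect at the plan's inputs is small.** Unsplit trials are unaffected, DBP is a secondary outcome, and PDQS power does not move.

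One could also enlarge the figures by assuming the interaction is tested at a looser level than 5%. The documents give no basis for that, so it carries no weight here.

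**Conclusion.** The point holds as an unresolved rule with a better alternative available at no cost. If the interaction test does choose the effect, and is run at 5% with a split between 50:50 and 80:20, the per-outcome false-positive rate is 8.0-8.3% under an either-gender rule and about 4.7% under a both-genders rule, against 5.0% if the pooled test always stands. The effect on DBP power ranges from a gain of about 1 percentage point to a loss of 3 to 4 points. The clearest consequence is that a sound pooled estimate could be dropped from the conclusion after a chance split.

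A reader might infer that the plan inflates its type I error. The documents do not support that, because they contain no success rule after a split. Nor do they support saying that the pooled effect will be discarded, that the primary outcome is underpowered, or that changing the rule would prevent spurious gender differences.

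**What to change.** Replace the sentence on combining men and women with:

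> For the primary and secondary outcomes, the primary estimate is the pooled intervention effect adjusted for gender, reported whatever the result of the interaction test; the intervention-by-gender interaction (tested at 5%) and gender-specific estimates with 95% CIs are supportive and do not alter the primary conclusion.

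Microbiome features should stay outside this sentence, as exploratory and under their own method. The change fits the design, since gender is already a stratification factor and a covariate. It is a free improvement: one sentence, no added participants or data, and every gender-specific result is still reported. If the sponsor already means the pooled effect to stand, the sentence simply records that. It should be settled before between-arm results are seen.
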